## List of Abbreviations

Abbreviation	Definition/Term
РР	Per Protocol
p.r.n	pro re nata (as necessary)
QA	Quality Assurance
QC	Quality Control
QMG	Quantitative Myasthenia Gravis (score)
SAD	Single Ascending Dose
SAE	Serious Adverse Event
s.c.	Subcutaneous
SUSAR	Suspected Unexpected Serious Adverse Reaction
TSC	Trial Steering Committee
ULN	Upper Limit of Normal

**Principal PIs Signatures:** 

By my signature, I confirm that my staff and I have carefully read and understand this protocol and agree to comply with the conduct and terms of the study specified herein.

Signature:

[name] Radboud University Medical Centre Nijmegen Netherlands

Signature:

Mu

Date: 11 November 2015.

[name] Radboud University Medical Centre Nijmegen Netherlands

Protocol AK-Study-578 - version 2.0 11 november 2015

CONFIDENTIAL

© Akari Therapeutics Plc

Protocol synopsis				
Protocol Title:	Coversin in paroxysmal nocturnal haemoglobinuria (PNH) in patients with resistance to eculizumab due to complement C5 polymorphisms.			
Protocol Number:	AK Study 578			
Sponsor:	Akari Therapeutics Plc			
	[name]			
	[name]			
	UK			
Investigational Product(s):	Coversin (rVA576) sterile solution for subcutaneous injection 7.2 mg/mL			
Phase of Development:	П			
Indication:	Paroxysmal nocturnal haemoglobinuria			
PI(s):	[name]			
	[name]			
	Department of Haematology			
	Radboud University Medical Centre			
	Nijmegen			
	Netherlands			
Study Center(s):	Radboud University Medical Centre			
	Nijmegen			
	Netherlands			
Objectives:	Primary Objective: Safety of Coversin (rVA576).			
	Secondary Objectives: Efficacy of Coversin in the treatment of patients with PNH resistant to eculizumab.			
Study Design:	Open label, non-comparative			
Planned Number of Subjects:	Minimally 1 and maximally 6			
	Patients with PNH, male or female, 18 years or older with proven resistance to eculizumab due to complement C5 polymorphisms			
Subject Population:				
Subject Population: Diagnosis and Main				
Diagnosis and Main Criteria for Inclusion and	resistance to eculizumab due to complement C5 polymorphisms			
Diagnosis and Main	resistance to eculizumab due to complement C5 polymorphisms Inclusion Criteria:			
Diagnosis and Main Criteria for Inclusion and	
 
resistance to eculizumab due to complement C5 polymorphisms
 
Inclusion Criteria:
 
Patients with known paroxysmal nocturnal haemoglobinuria (PNH)
 
			
Diagnosis and Main Criteria for Inclusion and	
 
resistance to eculizumab due to complement C5 polymorphisms
 
Inclusion Criteria: 
 
Patients with known paroxysmal nocturnal haemoglobinuria (PNH)
 
LDH ≥1.5 ULN
 
 
 
Resistance to eculizumab proven by both a recognised C5 polymorphism on genetic screening and complement inhibition on CH50 ELISA of <100% at concentrations of eculizumab in excess
 
			
Diagnosis and Main Criteria for Inclusion and	
 
resistance to eculizumab due to complement C5 polymorphisms
 
Inclusion Criteria: 
 
Patients with known paroxysmal nocturnal haemoglobinuria (PNH)
 
LDH ≥1.5 ULN
 
Resistance to eculizumab proven by both a recognised C5 polymorphism on genetic screening and complement inhibition on CH50 ELISA of <100% at concentrations of eculizumab in excess of 50µg/mL
 
 
 
			

## **Protocol synopsis**

	Exclusion Criteria:		
	• Pregnancy (females)		
	• Known allergy to ticks or severe reaction to arthropod venom (e.g. bee or wasp venom)		
	• Failure to satisfy the PI of fitness to participate for any other reason		
Treatment Regimen:	Single ablating dose of 0.57mg/kg per subject followed by daily maintenance doses. The initial maintenance dose will be 25% of the ablating dose. If this is insufficient to maintain complement activity at $\leq 10\%$ of baseline (pre-treatment) level after 5 days of treatment the daily maintenance dose will be increased by doubling until that level of inhibition is achieved. In the event of 100% inhibition being achieved the dose may be titrated downwards at the PI's discretion until a satisfactory clinical result is obtained. If at any point in treatment complement activity (CH50) is 50% of baseline or more a further ablating dose of 0.57mg/kg should be given. An increased daily maintenance dose may be required in the event of intercurrent infection or illness. CH50 level should be checked in the event of deteriorating clinical response manifested by rising serum LDH.		
Duration of Treatment:	Patients will undergo an initial period of 6 months treatment according to this protocol. At the expiry of this period, and on the recommendation of the PI, patients will have the option of remaining on long-term Coversin therapy and will enter the long term follow-up study.		
Endpoints:	Efficacy Endpoints:		
	Primary: Reduction in serum LDH from day 0 – Day 28		
	Secondary: Hb, haptoglobin, Fatigue (FACIT), Quality of Life (EORTC QL-C30), PNH RBC clone size, Transfusion requirement		
	Safety Endpoints:		
	Adverse events, ECG, Laboratory results, Vital signs.		
Statistical Methods:	Descriptive statistics		

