Single and repeat dose toxicology studies in rat and cynomolgus monkey have been performed using doses of up to 200 times (single dose) and 50 times (repeat dose) the expected human dose. In these studies no signs of toxicity were observed, no haematological or biochemical observations fell outside the range of normal and no gross or microscopic signs of pathology were found in any organ or tissue. It has therefore not been possible to set a No Observable Adverse Effect Level (NOAEL) and so a Human Equivalent Dose (HED) has not been established.

In pharmacology studies no toxicity has been observed to date in any species at any dose by any route of administration. These have included up to 50mg/kg intraperitoneally and up to 20mg/kg intravenously and by inhalation. The current

toxicology studies include single and repeat doses of up to 100 fold the likely HED (i.e. 57.0mg/kg in rats and primates).

The Phase I single ascending dose SAD study showed a maximum onset of action between 6 and 12 hours after injection and a slow recovery due to replenishment of C5 by the liver and other tissues so that at 96 hours post-dose CH50 had only returned to about 75% of baseline. This result was unexpected since both onset and duration of action in animals including NHP was substantially faster and it is considered likely that it is due to both a depot effect since humans generally have more subcutaneous adipose tissue than laboratory animals and because the production of C5 by the liver appears to be slower in humans.

The result suggests that, following a single ablating dose of Coversin, it should be possible to dose once a day using a maintenance dose between 25 and 50% of the ablating dose and keep terminal complement activity totally inhibited which is considered necessary in diseases such as PNH. If a fixed dose of 60mg, 50% higher than the 40mg needed to completely ablate C5 in a 70kg individual, is used it should provide adequate initial ablation in all subjects up to 100kg in weight. Similarly a daily maintenance dose of between 25 and 50% of this should be sufficient to provide 24 hour complement inhibition. Paediatric patients and patients of 50kg or less could be treated using a half dose.

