All patients will return to the hospital out patient clinic for follow-up at a minimum of monthly intervals according to the schedule in appendix 1.

Blood and urine samples will be taken from all patients according the schedule on appendix 1.

Patients who have satisfactorily mastered the technique of self-administration of Coversin may be discharged home when considered appropriate to do so by the PI providing that adequate arrangements for daily pre-dose blood sampling and sample handling for CH50 samples have been arranged (see below).

All patients will be followed up at a minimum of monthly intervals by the PI. If at the 6 month follow-up the patient wishes to continue Coversin treatment and if the PI is satisfied as to the suitability of Coversin treatment, the patient may be transferred to the long-term follow-up protocol.

It is expected that the majority of patients will respond to an ablating dose of 0.57mg/kg followed by a daily maintenance dose of 25% of the ablating dose.

On a per patient basis this will be adjusted as necessary on the basis of clinical response and CH50 assay. The protocol allows for a flexible, tailored dose adaptation on day 7 and any subsequent follow-up. in patients who are not adequately controlled as is outlined below ..

If patients are not adequately controlled at the first (7 day) or subsequent follow up either of three options may be followed:

Patient will be reinduced with an identical ablating dose (0.57 mg/kg) and /or the maintenance dose may be increased with one step at the time for a maximum of 2

times according to the below schedule of increments . Each incremental dose level must be given for a minimum of 4 days.

The definition of adequately controlled coversin treatment is:

LDH <1.5xULN AND CH50 <10% of baseline.

It is expected that this adequate control is achieved at day 5.

If a recent CH50 result is not available at the time of assessment then the PI will make a decision on clinical grounds alone on the adequacy or otherwise of disease control.

If adequate control is not achieved on day 5 of maintenance therapy at the standard dose level (and day 5 of increment dose levels if applicable) the following dose adaptation will take place:

- If CH50  $\leq 10\%$  and LDH is reducing but still  $\geq 1.5xULN$ , treatment at the same maintenance dose level is continued for another week.

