- If LDH is decreasing and if CH50 is between 50 and 10% of baseline, the maintenance dose may be increased according to the schedule of increments of maintenance dose shown below.
- If LDH is not reducing and CH50 is >50% of baseline the patient must either be discontinued from the trial and switched to alternative therapy or must be readmitted to hospital for dose stabilisation following another ablating dose (0.57mg/kg) of Coversin. In either case the findings and course of action must be discussed by a Trial Steering Committee comprised of, at minimum, the PI, and the Medical Director of the Sponsor company.

The schedule of increments for the maintenance dose is as follows:

Ablating dose	First maintenance	Second mainte-	Third mainte-
	dose level	nance dose level	nance dose level
0.57 mg/kg	0.14 mg/kg	0.29 mg/kg	0.57 mg/kg

Within each patient the first incremented maintenance dose should be given at 24 hour intervals for at least 4 days until steady state is reached and at that point a CH50 assay should be performed. If the CH50 is not  $\leq 10\%$  of baseline (adjusted to 100%) then the next incremental dose (Second maintenance dose level should be given for at least another 4 days before switching to the Third maintenance dose level. If at any

stage the CH50 is >50% of baseline another ablating dose should be given before using the next incremental dose.

[figure not shown]
Blood samples and timing is shown in Appendix 1. Samples for CH50, antibodies and drug level should be processed as shown in Section 20 and sent to the Akari Therapeutics Plc complement laboratory for assaying. All other laboratory tests should be done locally in the PI's hospital laboratory.

If an ablating dose is repeated , PK/PD and other assessment will be performed as indicated in Appendix 1 at 1hr, day 2 and day 5.

At increments of the maintenance dose PK and PD and other assessments are repeated at day 5 as indicated in Appendix 1.

Extra samples for PK/PD may be taken at the discretion of the investigators during illness or infection.

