## 13.6 Subjects to be Included in the Analysis

All patients in the study will be included in the safety analysis whether completing the trial according to the protocol or not. The efficacy analysis will include all measurements made whilst the patient(s) correctly followed the trial protocol.

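### The dose-adaptation rules conflict between the synopsis and Section 6.0 and within Section 6.0, which leaves open which LDH measurements Section 13.6 admits to the efficacy analysis

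*Combined protocol and SAP*

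**What the plan says.** **Synopsis, Treatment Regimen.** Titration follows CH50 alone. If activity is not at or below 10% of baseline after 5 days, "the daily maintenance dose will be increased by doubling until that level of inhibition is achieved". If CH50 is 50% of baseline or more at any point, "a further ablating dose of 0.57mg/kg should be given". Downward titration is left to the PI once inhibition is complete.

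**Section 3.0.** The maintenance dose can move in either direction, and the reader is sent to chapter 6 for the details.

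**Section 6.0.** Adequate control needs both LDH below 1.5×ULN and CH50 below 10%. For a patient not controlled "at the first (7 day) or subsequent follow up", the section offers re-induction and/or an increase: "the maintenance dose may be increased with one step at the time for a maximum of 2" times, on a ladder of 0.14, 0.29 and 0.57 mg/kg. It then says adaptation follows if control is not reached on day 5 of maintenance, and gives three bullets:
- CH50 at or below 10%, with LDH falling but still at least 1.5×ULN: same dose for another week.
- "If LDH is decreasing and if CH50 is between 50 and 10% of baseline": the dose *may* be increased.
- "If LDH is not reducing and CH50 is >50% of baseline the patient must either be discontinued from the trial", or be readmitted for another ablating dose. Either way the Trial Steering Committee must discuss the case.

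After the bullets come rules based on CH50 only. If CH50 is not at or below 10%, the next level *should* be given. If it is above 50%, an ablating dose comes first.

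**Section 6.2.** Once lyophilised drug is available, dosing moves to fixed multiples of 15 mg, with some room for individual adjustment.

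**Section 13.6.** Efficacy measurements are included if made "whilst the patient(s) correctly followed the trial protocol".

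**The concern.** The same laboratory result can lead to different actions depending on the sentence the investigator reads. In one state those actions range from a repeat ablating dose with continued treatment to leaving the trial. Safety is the primary objective, so this matters in itself.

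It also reaches the analysis. Section 13.6 makes entry to the efficacy analysis depend on correct conduct, and the protocol contains more than one version of correct conduct. The primary efficacy endpoint is LDH over Day 0 to Day 28. LDH is also one of the variables that steers dosing, and nobody is blinded. A judgement about adherence can therefore be made by people who already know the LDH values it would keep or remove.

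**Working it through.** **1. The ladder and the cap.** Inputs: ablating dose 0.57 mg/kg and first maintenance dose 25% of it (synopsis; Sections 3.0 and 6.0).
- 0.57 × 0.25 = 0.1425, printed as 0.14
- 0.57 × 0.50 = 0.285, printed as 0.29
- 0.57 × 1.00 = 0.57, printed as 0.57

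The printed ladder is exactly two doublings, so the synopsis and Section 6.0 agree up to the third level and part after it. Read literally, the synopsis continues to 0.57 × 2 = 1.14 mg/kg. Section 6.0 has no such level, and a patient on its third level with CH50 still at 10–50% is sent to a schedule with nowhere further to go.

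**2. The states side by side,** for a patient with LDH at or above 1.5×ULN. The permissive menu in Section 6.0 is available in every row.

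| LDH | CH50, % of baseline | Synopsis | Section 6.0 bullet | Section 6.0 CH50-only rules |
|---|---|---|---|---|
| falling | ≤10 | no increase | same dose, another week | not triggered |
| falling | 10–50 | *will* double | *may* increase | next level *should* be given |
| falling | >50 | double; ablating dose | none | ablating dose, then next level |
| not falling | ≤10 | no increase | none | not triggered |
| not falling | 10–50 | *will* double | none | next level *should* be given |
| not falling | >50 | double; ablating dose | discontinue, or readmit with ablating dose; committee discussion | ablating dose, then next level |

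The second and last rows conflict, both with the synopsis and inside Section 6.0. The fourth row has no specific instruction, only the menu. The bullets also omit the third and fifth rows, but the CH50-only rules cover those.

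**3. Boundaries.** At CH50 of exactly 50%, the synopsis gives an ablating dose, while Section 6.0 requires more than 50% and its second bullet treats 50% as part of the increment band. At exactly 10%, the synopsis target is met but the Section 6.0 definition of control is not. If LDH is also falling but still at least 1.5×ULN, the first and second bullets can both be read to apply.

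**4. Assessment day.** Section 6.0 places adaptation on day 7 in one paragraph and on day 5 of maintenance in another. The synopsis uses 5 days of treatment.

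**5. Downward steps.** The synopsis and Section 3.0 provide for them. Section 6.0, to which Section 3.0 refers, contains none.

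**6. Does this fall in the primary window?** Maintenance starts on day 2. Assume 4 to 5 days per level and no wait for results.
- Third level, earliest: 2 + 2×4 = day 10 to 2 + 2×5 = day 12
- A third doubling, if taken, earliest: 2 + 3×4 = day 14 to 2 + 3×5 = day 17

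All of these lie inside Day 0–28. As an illustration, take a patient with LDH falling and CH50 at 30% who is kept on the first level at the day 7 review. That is correct under *may* and incorrect under *will* or *should*. The status of the measurements over the remaining 28 − 7 = 21 days would then depend on the sentence chosen.

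**The case against.** The strongest reply is that a synopsis only summarises and Section 6.0 governs. No passage says so, and discarding the synopsis leaves the conflicts inside Section 6.0: *may* against *should*, the discontinuation bullet against the plain ablating-dose sentence, <10% against ≤10%, and day 5 against day 7.

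Other replies have force:
- Re-ablation is one of the two branches of the discontinuation bullet, so the passages overlap. What differs is the option to discontinue, the readmission and the committee discussion.
- Day 5 and day 7 might be reconciled by the visit schedule, which is not visible in the text available. Section 6.0 also lets the PI decide on clinical grounds when no recent CH50 result is to hand.
- Section 13.6 can be read as concerning patient compliance, as in Section 11.0, and not the investigator's choice of dose. That reading is reasonable, but the section does not state it.
- Under Section 6.2 the mg/kg ladder may apply mainly to the first patient.

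A reader might infer more than the documents support:
- That one state has no rule at all. The menu reaches it, and a patient with LDH below 1.5×ULN and CH50 below 10% already counts as controlled.
- That the problem is one conflicting state and one empty state. The table shows more conflict than that and no truly empty state.
- That the 4-day minimum is a rival decision day. It is a minimum duration per level.
- That Section 1.4, with "keep terminal complement activity totally inhibited which is considered necessary in diseases such as PNH", contradicts the 10% target. That sentence is dose rationale, not an operating rule.
- That a disputed patient costs one sixth (17%) of the efficacy data. Section 13.6 selects measurements, not patients, so earlier measurements stay in.

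**Conclusion.** The point holds. The plan gives conflicting instructions on the cap, on the action at CH50 above 50% with LDH not falling, on whether an increase at 10–50% with LDH falling is obligatory, on both thresholds, and, subject to the unseen schedule, on the assessment day. Two further items are unspecified: LDH not falling with CH50 at or below 10%, and how a downward step is made.

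The largest numerical divergence is 1.14 against 0.57 mg/kg. It arises only if the synopsis wording is followed past the third level. The effect on the LDH result cannot be calculated from the documents; what can be shown is that the decisions fall within Day 0–28. The analysis consequence assumes that Section 13.6 could be applied to investigator dosing decisions, which its wording does not rule out. No view is taken on which clinical rule is right.

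**What to change.** The sponsor and clinical team should reconcile the synopsis, Section 3.0, Section 6.0 and the fixed-dose regimen of Section 6.2 into one decision table in Section 6.0. It should cover every LDH/CH50 state including the boundary values, and give one assessment day, one limit on steps and one provision for downward change. The synopsis should refer to that table instead of restating the rules; Section 3.0 already points to chapter 6. The content of each cell is for the clinical team to decide.

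Section 13.6 should state that measurements made after a dose adaptation, a repeat ablating dose or another investigator dosing decision remain in the efficacy analysis.

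This changes protocol wording only. It adds no patients, visits or assays.

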## List of prohibited medications:

- 1. Tizanidine (if on ciprofloxacin)
- 2. Eculizumab (*Soliris*®) should be discontinued before Coversin therapy is commenced. Ideally this should be 2 or more weeks before commencing Coversin unless, in the opinion of the investigator, it would not be in the best interests of the patient to do so.

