#### 3.0 TRIAL DESIGN

Treatment with Coversin comprises an ablating dose on day 1 and daily maintenance treatment from day 2 onwards. Calculated according to body weight, the ablating dose will be 0.57mg/kg. Thereafter the daily repeat maintenance dose will be titrated according to clinical response and complement inhibition as determined by CH50 ELISA. The initial daily maintenance dose will be 25% of the ablating dose (0.14 mg/kg) and this will be adjusted up or down if necessary once steady state is reached (5 days). This is further explained in chapter 6, TRIAL PROCEDURE .

In order to mitigate the risk of infection by *Neisseria sp* all subjects or patients taking part in the trial will be carefully instructed about precautions to be taken in case of actual or suspected infection. Patients may either be given permanent antibiotic prophylaxis (oral penicillin daily) or be provided with high dose ciprofloxacin and instructed to immediately commence taking it in the event of a suspected infection. In the latter case they will also be told to make immediate contact with the PI or her deputy. In addition all patients will receive immunisation with quadrivalent meningoccal vaccine Anti meningococcal B vaccine has recently been developed and will be given once approved in the country where the patient is treated. Vaccination against meningococci typ ACW135Y is required at the start of the study. Should the first vaccination take place  $\leq 14$  days of commencement of Coversin, then the patient must take high dose antibiotic for the first 2 weeks. This will generally be ciprofloxacin daily (2x 750mg orally, until 2 weeks have elapsed since first vaccination) or alternative antibiotic treatment directed against meningococci.

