#### 9.1 Inclusion Criteria

- Males or females taking adequate contraceptive precautions if of childbearing potential, 18 80 years of age
- Body weight  $\geq$ 50kg and  $\leq$  100kg
- The patient has provided written informed consent.
- Willing to avoid prohibited medications for duration of study (see Exclusion Criteria)
- Must agree to take appropriate prophylactic precautions against Neisseria infection
- Must be counselled regarding the possible reproductive risks of using Coversin and be advised to use an adequate method of contraception pending further data on reproductive toxicology.

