#### 9.2 Exclusion Criteria

- Body weight <50kg or >100kg
- Pregnancy

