#### 10.0 NEISSERIA IMMUNISATION AND ANTIBIOTIC PROPHYLAXIS

It is known that the products of C5 complement activation are important in protection against infection by *Neisseria* species (15). This is believed to be the only known hazard of blocking this stage of the complement cascade and patients taking part in previous trials of complement C5 inhibitors were found to be at greater risk of *Neisseria* infection, particularly meningococcal infection (16). For this reason all patients entering the trial should where possible have received immunization against *Neisseria meningitidis* infection in the past, or must receive a booster shot of quadrivalent vaccine (against meningococci type ACW135Y) ) at the time of recruitment into the trial and at least prior to receiving the first dose of medication. In addition all patients should be immunised against Meningitis B using the *Bexsero*® vaccine as soon as this vaccine is available in the country where the patient is treated. This vaccine requires an initial dose followed by a booster 1 month later.

All patients will in addition have throat and nasal swabs taken after entry to the trial and prior to receiving the first dose. Cultures positive for any *Neisseria* species will not be grounds for excluding that subject from the trial but will alert the PI to use extra vigilance during and after induction of complement inhibition. Any patient having positive nasal swabs will be retested 7 days later to ensure that the pathogen has been eliminated by ciprofloxacin.

Patients will preferably receive a 5 day course of oral ciprofloxacin commencing the day before the first dose of Coversin and this will either be followed by oral penicillin prophylactic treatment or, at the discretion of the PI and in accordance with local custom, the patient may be provided with high dose ciprofloxacin to be started in the event of an actual or suspected infection. Patients will be instructed to make urgent contact with the PI or her deputy in that event.

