Because of the known drug interaction between tizanidine and ciprofloxacin the former drug will be prohibited during this trial. In addition patients will be given a medication leaflet for ciprofloxacin in their native language in which other possible drug interactions (e.g. with antacids) and precautions regarding known or suspected sensitivity to fluoroquinolones will be pointed out. It is the responsibility of the PI and her deputies to make the patient(s) aware of these precautions.

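### The prohibited-medication list bars tizanidine only while a patient is on ciprofloxacin, whereas Section 10 bars it throughout; a minor safety-text mismatch that the list should be edited to remove

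*Combined protocol and SAP*

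**What the plan says.** Two places in the protocol set a rule on tizanidine.

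- The List of prohibited medications, which follows the synopsis, has two entries. The first is "Tizanidine (if on ciprofloxacin", closed by a bracket. The second is eculizumab, which is to be stopped before Coversin starts, ideally by two weeks or more, with the investigator free to judge otherwise.
- Section 10 states: "Because of the known drug interaction between tizanidine and ciprofloxacin the former drug will be prohibited during this trial". No condition is attached. It adds a ciprofloxacin leaflet in the patient's own language and says: "It is the responsibility of the PI and her deputies to make the patient(s) aware of these precautions".

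Ciprofloxacin can enter a patient's treatment in several ways. Section 10 prefers a 5-day course starting the day before the first Coversin dose. Section 3.0 generally calls for it, or an alternative, when meningococcal vaccination was recent. After that, a patient either takes daily oral penicillin or holds a standby supply. Under Section 3.0 the standby patient may "be provided with high dose ciprofloxacin and instructed to immediately commence taking it in the event of a suspected infection". Section 10 gives the same option: "the patient may be provided with high dose ciprofloxacin to be started in the event of an actual or suspected infection". Both sections also tell this patient to contact the investigator or deputy without delay.

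Section 9.1 makes avoidance of prohibited drugs an inclusion criterion: "Willing to avoid prohibited medications for duration of study (see Exclusion Criteria", again closed by a bracket.

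**The concern.** The two rules concern the same drug and differ in scope, and the narrower one stands under the title a reader would consult to check a concomitant medicine. A patient holding unopened standby ciprofloxacin is not, in ordinary language, on it. Someone who took the list entry as the specific rule, qualifying the general statement in Section 10, could let that patient use tizanidine. A suspected infection would then lead the patient to start ciprofloxacin at home, unplanned, while taking the drug with which it interacts. That interaction is the protocol's own reason for the ban.

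A clerical fault makes the rule harder to find. The cross-reference in Section 9.1 sends the reader to exclusion criteria that name no medication.

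**Working it through.** No arithmetic applies, and the protocol gives no figure to reproduce. The check is to set the texts side by side.

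**Step 1. Compare the two tizanidine rules by ciprofloxacin status.**

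- *Taking ciprofloxacin* (starting course, post-vaccination cover, or standby supply already begun): the list bars tizanidine, and so does Section 10. They agree.
- *Holding standby ciprofloxacin, not started*: the list read literally does not bar tizanidine; Section 10 does. They differ, and the patient may start ciprofloxacin without notice.
- *On penicillin, holding no ciprofloxacin*: the list does not bar tizanidine; Section 10 does. They differ, but the patient has no supply with which to start ciprofloxacin unplanned.

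Only the second situation carries the hazard that Section 10 gives as its reason.

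**Step 2. Can the two texts be reconciled?** Reading the list's condition generously, to cover a patient who merely holds ciprofloxacin, removes the difference in the second situation but not in the third. The texts therefore differ under either reading. They are nested, however: anyone who follows Section 10 also satisfies the list. The conflict causes harm only if the list is taken to override or qualify Section 10.

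**Step 3. Follow the Section 9.1 cross-reference.**

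- Section 9.2 has two entries: "Body weight <50kg or >100kg", and pregnancy.
- The synopsis has three: pregnancy; "Known allergy to ticks or severe reaction to arthropod venom (e.g. bee or wasp venom", closed by a bracket; and the investigator's judgement of fitness.

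None of these 2 + 3 = 5 entries names a drug. The cross-reference reaches neither tizanidine nor eculizumab. Both stand in the List of prohibited medications, which has its own line in the table of contents.

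**Step 4. Bound the number affected.** The synopsis and Sections 1.6 and 6.0 cap enrolment at 6. The documents give no frequency for tizanidine use or for choice of the standby option. The number of patients in the hazardous situation therefore lies between 0 and 6, and 0 is quite possible.

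**The case against.** The strongest reply is that the protocol already handles this. Section 10 bans tizanidine outright, explains why, and makes the investigator and deputies responsible for telling patients about the ciprofloxacin precautions. A protocol is read as a whole, and the list does not say that tizanidine is otherwise allowed. A standby patient who starts ciprofloxacin must also contact the investigator or deputy at once, so a clinician should hear of it quickly.

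Most of this stands, and it is why the point is minor. Two limits remain. First, the instruction is to start ciprofloxacin immediately; nothing makes the first tablet wait for the investigator's advice. Second, the leaflet is described as covering other interactions, so for tizanidine the stated safeguard is the ban itself, which the list words more narrowly.

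It is also fair to say that the Section 9.1 slip has little practical effect. The list is titled, indexed and easy to find, and the requirement to avoid prohibited drugs is intact.

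A reader might go further in two directions that the documents do not support. One is to infer that the protocol leaves patients unprotected against the interaction; Section 10 rules that out. The other is to infer from the faulty cross-reference that the listed drugs ought to be exclusion criteria. Section 9.1 asks only for willingness to avoid them, and eculizumab has only to be discontinued before Coversin, with discretion over the interval.

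**Conclusion.** The inconsistency is real and minor. The list makes the tizanidine ban conditional on ciprofloxacin use, while Section 10 makes it unconditional. The difference matters for safety only in a patient who holds standby ciprofloxacin, and only if the list is treated as the governing rule. Section 10 and the prompt-contact instruction both reduce the risk. At most 6 patients could be concerned and possibly none. No endpoint, sample size or analysis changes.

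The conclusion rests on two readings: that being on ciprofloxacin means taking it, not merely holding it, and that Section 10 states the intended rule. The second is supported by Section 9.1, which asks for avoidance over the whole study. The cross-reference error is clerical and adds no risk of its own. The point is still worth correcting because the protocol itself names the interaction and the correction costs almost nothing.

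**What to change.** 1. In the List of prohibited medications, delete the bracketed ciprofloxacin condition so that the entry reads simply as tizanidine and matches Section 10. This restates an existing ban and loosens nothing. Narrowing Section 10 to the list's wording instead would leave standby patients exposed to the interaction.
2. As an editorial correction, change the bracket in Section 9.1 so that it refers to the List of prohibited medications instead of the exclusion criteria.
3. Do not copy the drugs into Section 9.2. That could turn away a tizanidine user who is willing to stop, and could confuse the handling of patients who have recently come off eculizumab.

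The cost is two wording edits. The clinical downside falls on a tizanidine user on penicillin prophylaxis who holds no ciprofloxacin: that patient must stop or switch although the stated reason for the ban does not apply to them at that time. Section 10 already requires this, so the edit adds no new burden.
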